We aim to understand which messaging strategies are most successful at communicating information about Covid-19 to underserved communities. The goal is to understand how to best structure messaging to make them more impactful. We are measuring "impact" as a) trust in information coming from the healthcare system; b) attention and retention of key facts about Covid-19 presented in the videos; c) interest in following the advice in the videos pertaining to social distancing, hygiene and mask-wearing;

¹See Appendix Section A for transcripts of the videos.

and d) health-seeking behavior.

We hypothesize that overall videos delivered by concordant messengers will be more effective. Moreover, acknowledging the “elephant in the room” –i.e., explicit acknowledgment of inequalities – will make the videos more impactful, especially for discordant doctor messengers. We also hypothesize that videos delivered by our partner doctors (even of discordant race or ethnicity) will be more impactful than one delivered by a representative of the CDC. Finally, for individuals who believe that mask wearers are likely to be viewed as sick or up to no good by larger than what we are informing them, we predict that presenting information about beliefs will increase demand for mask wearing.

2. Treatments, and Experimental Protocols

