3. Does addressing the “elephant in the room” lead to greater video impact?
4. Are the doctors in our videos more effective at communicating the same message with underserved populations than [name], a representative of the CDC and the US federal government’s response? (To test this hypothesis, we will focus on the outcomes associated with the social distancing and hygiene video.)
5. Does the [name] video lead to a "shut down" and refusal to pay attention to the rest of the message: for this we can compare the attitude to masks (which are not mentioned in the [name] video, and are discussed in a video segment shown after that with [name]).
6. Does providing information on perceptions about mask wearers change an individual’s willingness to wear a mask? We proxy for willingness to wear a mask in two key ways: a) demand for information about mask-making, b) incentivized allocations of money to support masks for black or latinx communities vs. other charitable projects targeted at the same communities.
 - (a) Focus groups and baseline data suggest that on average, members of the black community worry that they will be viewed as “up to no good” when wearing a mask by a larger percent of Americans than actually hold that belief. For Latinx communities, the fear is more that mask-wearers will be perceived to be sick, generating a different kind of stigma.
 - (b) Specifically, we predict that the effects of the “social norm debiasing” treatment should vary with the respondent’s priors about how mask-wearers are viewed. Individuals learning that their beliefs were too pessimistic should increase their willingness to wear a mask, while those learning that their beliefs were too optimistic (this should be rare) might respond the opposite way.

Secondary hypotheses involving specific interactions between treatments:

1. Racial concordance might also give more credibility to other information presented in the videos such as info delivered by [name] of the CDC or information about mask perceptions.
2. Does addressing the “elephant in the room” increase impact of the videos more for discordant doctor messengers?
3. Does acknowledging the “elephant in the room” give greater credibility to other information in the video, such as the CDC video or the mask debiasing information? (Interaction effects with CDC treatment and with mask debiasing treatment.)

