5.3 Regression Analysis

We will do two types of analysis: identifying effective videos in our sample, and general tests of the hypotheses described above.

- Best treatment

We are interested in selecting the best combination of types of video for scale up. In order to identify the most effective combination of videos, we will adapt a disciplined pooling methods of Banerjee et al (2020) for selecting the most effective combination of treatments (to a settings were we have large

sample within each of 16 treatment cells), and Andrews et al (2020) to correct for small sample bias in estimating the impact the most effective method.⁶

For this specific question of whether *our* messages of a given type (concordant race, correcting priors, etc), since random assignment is done by individuals, we do not adjust standard errors. This is the correct analysis for scaling up these videos per-se.

- Hypothesis tests

In order to test the hypotheses listed above, we run the following contrasts (Hispanic and Black will be run separately for all the contrasts:

Main hypotheses tests:

1. Is there any impact of the videos (treatment vs control)
2. Concordant vs. discordant messengers: pooled across all
3. [name] with "no elephant" and the two different versions of "elephant in the room", no [name] each compared to the "no elephant, no [name]" condition
4. [name] versus everything else.
 - For social distancing and hygiene (largest effect expected here for the [name] treatment)
 - For other outcomes
5. Mask-debiasing treatment on mask outcomes, heterogenous based on respondent prior beliefs (lower or higher than 8 out of 10 people think mask wearer is helping the community).

Secondary hypotheses tests

1. [name] treatment effects will be interacted with concordant doctor
2. [name] treatment effect will be interacted with social debiasing treatment (which may be less effective after presenting [name])
3. Elephant treatment will be interacted with concordant doctor
4. Mask treatment effect will be interacted with concordant doctor
5. Mask treatment effect will be interacted with elephant treatment
6. [name] treatment effect will be interacted with elephant treatment
7. Gender of provider will be interacted with concordant doctor and/or respondent gender

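### Two analyses in Section 5.3 do not fit Figure 1: the CDC-by-elephant interaction cannot be estimated, and contrast 4 mixes messenger with Video 1 content

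*Combined protocol and SAP*

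**What the plan says.** Section 3, main hypothesis 4, asks "Are the doctors in our videos more effective at communicating the same message with underserved populations than [name" of the CDC (the name is masked in the public text), and directs the test to social distancing and hygiene outcomes. Main hypothesis 5 asks whether the CDC video puts respondents off the mask material that follows. Neither hypothesis names its comparison arms.

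Section 5.3 lists the contrasts:

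- Contrast 3 takes the CDC video without elephant content, and each elephant version with a partner doctor, "each compared to the 'no elephant, no [name]' condition". It names no outcomes.
- Contrast 4 is "name] versus everything else". Its first line reads "For social distancing and hygiene (largest effect expected here for the [name] treatment"; its second covers all remaining outcomes.
- Secondary test 6 is "name] treatment effect will be interacted with elephant treatment".

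Secondary hypothesis 3 in Section 3 asks whether elephant content will "give greater credibility to other information in the video, such as the CDC video or the mask debiasing information", and says this means interactions with both the CDC and the mask treatments.

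Figure 1 has four content columns (doctor-delivered message, CDC-delivered message, Elephant 1, Elephant 2), two mask levels, and concordant or discordant doctors. Section 5.3 counts a large "sample within each of 16 treatment cells". The listed controls are strata, race/ethnicity and language choice. No indicator for elephant content is among them, and no regression equation is printed.

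**The concern.** An interaction needs cells in which both factors are present. If the CDC and elephant columns exclude each other, test 6 has no data behind it.

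Hypothesis 4 holds the message fixed and varies the messenger. Contrast 4 varies more than that: its comparison pool includes arms with different Video 1 content. If that content affects what people retain or intend after Videos 2 and 3, contrast 4 credits the effect to the partner doctors. The plan treats this as possible. The Introduction predicts that acknowledging inequalities "will make the videos more impactful, especially for discordant doctor messengers", and secondary hypothesis 3 asks about spill-over to the later videos. At stake is a conclusion that doctors outperform the CDC representative when part or all of the difference comes from Video 1.

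**Working it through.** **Cell count.** Figure 1 gives 4 columns x 2 mask levels x 2 concordance levels = 16, which matches the count in Section 5.3. Crossing all four listed aspects would give 2 x 3 x 2 x 2 = 24, which does not match. So CDC delivery and elephant content never occur together. Of the 16 cells, 4 are CDC (2c/d, 6c/d), 4 are doctor without elephant (1c/d, 5c/d), and 8 are doctor with elephant (3, 4, 7, 8, each c/d).

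**Test 6.** Over the 16 cells, build columns for intercept, concordance, mask, CDC, Elephant 1, Elephant 2 and CDC x elephant. The last is zero in every row. The matrix has 7 columns and rank 6, so the interaction cannot be estimated under any assumption about effects or allocation.

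**What contrast 4 estimates.** Let t be the CDC-minus-doctor effect, and e1, e2 the effects of the two elephant versions on the outcome. With equal cells the 12 comparison cells average (4 x 0 + 4 x e1 + 4 x e2)/12 = (e1 + e2)/3 above the doctor, no-elephant cells. Contrast 4 therefore estimates t - (e1 + e2)/3, or t - (2/3)e when e1 = e2 = e. The matched comparison in contrast 3 (2c/d + 6c/d against 1c/d + 5c/d) estimates t.

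**Precision.** From Section 2.2: 10,000 Black and 5,000 Hispanic respondents. Assumed, because the documents do not give them: 17 equal cells (16 plus pure control), SD 1, two-sided unadjusted 0.05, individual-level standard errors. SE = sqrt(1/n1 + 1/n2).

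| | Black | Hispanic |
|---|---|---|
| Per cell | 588 | 294 |
| Contrast 4: n1, n2 | 2,353, 7,059 | 1,176, 3,529 |
| Contrast 4: SE | 0.0238 | 0.0337 |
| Matched: n1, n2 | 2,353, 2,353 | 1,176, 1,176 |
| Matched: SE | 0.0292 | 0.0412 |

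**Rejection by contrast 4 when t = 0.** Shift = -(2/3)e and rejection = P(|Z + shift/SE| > z), with z = 1.960, or 2.638 for 0.05/6. The second column of each pair uses Bonferroni over the six outcome families in Section 5.2. That method is assumed; the plan promises adjustment but names none.

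| Carry-over e (SD) | Shift | Black, 0.05 | Black, 0.05/6 | Hispanic, 0.05 | Hispanic, 0.05/6 |
|---|---|---|---|---|---|
| 0 | 0 | 5% | 0.8% | 5% | 0.8% |
| 0.01 | -0.007 | 6% | 1.1% | 5% | 1.0% |
| 0.05 | -0.033 | 29% | 11% | 17% | 5.0% |
| 0.10 | -0.067 | 80% | 56% | 51% | 26% |

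Example (Black, e = 0.05): 0.0333/0.0238 = 1.40, so rejection is 29%. The matched comparison contains no elephant term, so carry-over does not move it from its nominal level.

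**The case against.** The strongest reply is that no analysis is missing. Contrast 3 is itself a main test. It gives the matched CDC comparison and also both elephant effects against the same reference, so the elephant component of contrast 4 can be read from planned output. At 0.10 SD each elephant effect would be detected with about 93% power (Black) or 68% (Hispanic); at 0.05 SD this falls to about 40% or 23%. This objection stands and is the main reason the point is minor.

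Pooling is also a declared choice in Section 3, and contrast 4 is a valid randomised comparison of packages. A reader might infer that it is biased or wrong. It is not; it answers a different question from Hypothesis 4, and only if carry-over exists. The prediction in the Introduction does not name social distancing or hygiene, and secondary hypothesis 3 is a question.

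The rates above also leave out the doctor-video random effect that Section 5.3 plans for general conclusions. If it made the standard error 1.25 or 1.5 times larger (assumed), the 29% would become 20% or 15%, and the 17% would become 12% or 10%.

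A reader might further infer that the pure control sits in the comparison pool. The text does not say so, and Hypothesis 4 compares the CDC representative with doctors seen in videos.

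None of this rescues test 6. Contrast 3 can show whether elephant content improves response to the doctor-delivered Video 2, but that is not an interaction with CDC delivery.

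**Conclusion.** The point holds, and it is minor. The failure of test 6 and of the CDC half of secondary hypothesis 3 follows from Figure 1 alone and needs no assumption. The mixing of messenger and content in contrast 4 also follows from Figure 1, on the natural reading that no elephant indicator enters the model; the two-thirds weight needs equal cells. Its practical size is unknown: nil without carry-over, negligible at 0.01 SD, material at 0.05 SD and above.

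A reader might go further and conclude that the plan lacks a clean messenger test, or that a false claim about doctors is likely. The documents support neither. The clean comparison is planned, and they give no carry-over size from which to judge likelihood.

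**What to change.** 1. Delete secondary test 6, and restrict secondary hypothesis 3 to the interaction with mask debiasing.
2. State that, for Hypotheses 4 and 5, the messenger effect on social distancing and hygiene outcomes and on mask outcomes is read from the matched part of contrast 3: cells 2c/d + 6c/d against 1c/d + 5c/d, pure control excluded. Fitting contrast 4 among the video cells with both elephant indicators is equivalent.
3. Keep contrast 4 as a pooled package comparison, not read as a messenger effect, and say whether the pure control is in it.
4. Show the language split from Section 5.4 beside the matched result. The CDC video is always in English, so for respondents who chose Spanish the matched comparison still mixes messenger with language.

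This is wording only and needs no new data. The cost is precision: 0.0292/0.0238 = 1.22, so the standard error is 22% larger. The effect detectable with 80% power, (1.960 + 0.842) x SE, rises from 0.067 to 0.082 SD (Black) and from 0.094 to 0.116 SD (Hispanic). For a true messenger effect of 0.08 SD and no carry-over, power is 78% matched against 92% pooled (Black), and 49% against 66% (Hispanic).

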2.1 Treatments

Each subject watches three videos. Each video features a different doctor. All partner doctors viewed in the videos by a given subject are of the same racial or ethnic background.²

1. Video 1:

- Introduction
- Discussion of symptoms
- Acknowledgement of “elephant in the room” issues, where applicable.

2. Video 2:

- Information about social distancing and hygiene

3. Video 3:

- Information about masks

We are varying four aspects of the videos across treatments:

1. Racial or ethnic concordance with partner doctors in the videos (note that we side-step the issue of language: for Spanish speakers, they can chose English or Spanish, and there are non ethnically Hispanic doctors speaking in Spanish).³
2. Video 1 content: Elephant in the room
 - No elephant in the room content
 - Elephant in the room 1: Trust or Fear
 - Elephant in the room 2: Economic Inequality

²However, some individuals may see two black doctors and [name] from the CDC, a white doctor and representative of the US government.

³However we do not have recordings in other languages.

3. Identity of the doctor delivering Video 2

- Pre-recorded video of [name] of the CDC in front of the White House
- Partner doctor

4. Video 3 content: mask debiasing

- Basic mask information, no perceptions information
- Basic mask information, perceptions information
 - For the latinx community, the video discusses perceptions that the mask-wearer is sick.
 - For the black community, the video discusses perceptions that the mask-wearer is “up to no good.”
 - In both cases the message reports responses from a prior survey of perceptions that mask wearers in photos of the same racial/ethnic group are “protecting the community.”

All of the video scripts can be found in Appendix Section A. Figure 1 shows how these different treatments are incorporated in the randomization design.

Figure 1: Treatment Design: There are 8 content-variants for each video, shown here. Cell 1c/d includes the baseline information package. For each combination of message content, the partner doctors in the video may either be of a concordant (c) or discordant (d) racial/ethnic background.

All treatments receive basic information +	Doctor-Delivered CDC Message	[name] -Delivered CDC Message	Elephant 1: Fears (L) or Trust (A)	Elephant 2: Economic Inequality
No Mask Debiasing	1c/d	2c/d	3c/d	4c/d
Mask Debiasing	5c/d	6c/d	7c/d	8c/d

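### On Video 2 and social distancing/hygiene outcomes, the CDC-speaker × concordance interaction (Section 5.3, secondary test 1) does not estimate the credibility carry-over in secondary hypothesis 1

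*Combined protocol and SAP*

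**What the plan says.** **Hypothesis.** Section 3, secondary hypothesis 1, states: "Racial concordance might also give more credibility to other information presented in the videos such as info delivered by [name] of the CDC". It goes on to name the mask-perception information as a second example. The part about the CDC speaker is a carry-over claim: the same federal message should be believed more when the surrounding doctors are concordant.

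**Test.** Section 5.3, secondary test 1, reads "name] treatment effects will be interacted with concordant doctor". It names no comparator cells, outcomes or expected sign. Main test 3 compares the CDC-speaker condition with the condition that has neither an elephant message nor the CDC speaker (cells 1 and 5 of Figure 1). Main test 4 is "name] versus everything else".

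**Design.** Section 2.1 states: "All partner doctors viewed in the videos by a given subject are of the same racial or ethnic background". Under Figure 1, "the partner doctors in the video may either be of a concordant (c) or discordant (d) racial/ethnic background". One option for Video 2 is "Pre-recorded video of [name] of the CDC in front of the White House", which is a single recording. Footnote 2 accepts the resulting mix: "some individuals may see two black doctors and [name] from the CDC".

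**Expectation.** Section 1 states: "We hypothesize that overall videos delivered by concordant messengers will be more effective". No effect size is given.

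**The concern.** The factor called concordance does not change the same things on the two sides of the interaction. In cells 2c/d and 6c/d it changes the doctors in Videos 1 and 3 and leaves Video 2 untouched. In every other video cell it changes the doctors in Videos 1, 2 and 3. The interaction therefore subtracts a quantity that includes the direct effect of a concordant doctor delivering Video 2, and hypothesis 1 says nothing about that effect.

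The plan expects this direct effect to be positive. If it is, the interaction falls below the carry-over of interest and may be null or negative while the carry-over is real. A report that took the interaction as the answer to secondary hypothesis 1 could say that concordance fails to help the CDC message, or weakens it, when the randomised CDC-speaker cells show a benefit.

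**Working it through.** The documents give no power, effect size or expected value for this test, so there is no stated figure to reproduce. The structural counts agree: 8 content variants × 2 = 16 cells, and 10,000 + 5,000 = 15,000 respondents.

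**1. What each difference contains (Video 2 or SD-H outcome).**

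- k: carry-over from concordant doctors in the other videos to the CDC speaker's Video 2.
- s: the same carry-over to a doctor-delivered Video 2.
- d: direct effect of a concordant rather than discordant doctor delivering Video 2.

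| Cells | Video 2 messenger, c v d | Concordant − discordant |
|---|---|---|
| CDC speaker (2, 6) | same clip | k |
| Comparator (1, 5, or all 12 other video cells) | concordant v discordant doctor | d + s |

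Interaction = k − (d + s). A least-squares fit to the implied cell means returned this with either comparator set.

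**2. Sign over a range of values.**

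| d | k | Interaction if s = 0 | Interaction if s = k |
|---|---|---|---|
| 0.10 | 0 | −0.10 | −0.10 |
| 0.10 | 0.05 | −0.05 | −0.10 |
| 0.10 | 0.10 | 0.00 | −0.10 |
| 0.05 | 0.10 | +0.05 | −0.05 |
| 0.10 | 0.20 | +0.10 | −0.10 |

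The difference within the CDC-speaker cells equals k in every row. If s = k the interaction is −d whatever k is.

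**3. Precision.** Assumed, because the plan does not state them: 17 equal arms (16 cells plus control), SD 1, two-sided 0.05, no multiplicity adjustment. The group sizes are from Section 2.2, and Section 5.3 runs each contrast separately by group.

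- Black sample: 10,000/17 = 588 per cell, so two cells hold 1,176.
- Within-CDC-speaker contrast: SE = √(2/1,176) = 0.041.
- Interaction against cells 1 and 5: SE = √(4/1,176) = 0.058.
- Hispanic sample: 5,000/17 = 294 per cell; the SEs are 0.058 and 0.082.

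**4. Chance of each result with k = d = 0.10**, normal approximation, for example Φ(0.10/0.058 − 1.96) = 0.40:

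| | Black | Hispanic |
|---|---|---|
| Interaction significantly negative, s = 0 (expectation 0) | 2.5% | 2.5% |
| Interaction significantly negative, s = k (expectation −0.10) | 40% | 23% |
| Within-CDC-speaker contrast significantly positive (expectation +0.10) | 68% | 40% |

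**5. Sensitivity.** With a control share from 0 to 20% and s = k, the chance of a significant negative interaction runs from 42% to 35% (Black) and from 24% to 20% (Hispanic). The chance of a significant positive within-CDC-speaker contrast runs from 71% to 61% and from 42% to 35%. With all 12 other video cells as comparator and 17 equal arms, the interaction SE in the Black sample is √(2/1,176 + 2/(6 × 588)) = 0.048, and the chance of a significant negative result at s = k is 56%.

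**The case against.** A reader might infer that the interaction must turn negative once concordance works, so that support for main hypothesis 2 counts automatically against secondary hypothesis 1. The documents do not support that. The result −d needs carry-over to a doctor-delivered Video 2 to equal carry-over to the CDC speaker, and nothing in the plan says so. A concordant doctor may need less borrowed credibility than a federal representative. With s = 0 and k above d the interaction stays positive. Main test 2 also pools all videos, so a positive result there can come from Videos 1 and 3 with d = 0.

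Three further points on the other side stand in part:

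- The carry-over is not out of reach. In a regression with both main effects it is the concordance coefficient plus the interaction coefficient. What is missing is its naming as a contrast.
- The interaction answers a legitimate question, and Section 3 introduces these hypotheses as interactions. Three secondary hypotheses face seven secondary tests, so the pairing of test 1 with hypothesis 1 is inferred, though it is the natural one.
- Secondary test 1 sets no outcome limit. For outcomes tied only to Videos 1 or 3, such as mask outcomes, the direct Video 2 messenger difference does not arise.

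None of this makes the interaction an estimate of k on Video 2 or SD-H outcomes.

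**Conclusion.** The point holds for Video 2 and SD-H outcomes and for indices that include them. There, secondary test 1 estimates k − (d + s), which is lower than the carry-over by d + s. This follows from the design in Section 2.1 and does not depend on the assumed effect sizes. The sign and the probabilities do. At k = d = 0.10, the chance of a significant result in the wrong direction spans 2.5% to 40% in the Black sample and 2.5% to 23% in the Hispanic sample, as s goes from 0 to k. Even at the favourable end the interaction has expectation 0 although the true carry-over is 0.10. The adjustment for multiple outcomes promised in Section 5.2 is not reflected in these figures.

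The randomisation and data collection are sound. The defect is confined to which contrast is pre-specified for one secondary hypothesis, but it can reverse what is concluded about that hypothesis, so it should be corrected before analysis.

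**What to change.** In Section 5.3, add as the test of secondary hypothesis 1, so far as it concerns the CDC speaker, concordant v discordant within the CDC-speaker cells: 2c + 6c v 2d + 6d, or equivalently the concordance plus interaction coefficients. State that a positive value supports the hypothesis.

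Lead with the ratings and intentions collected straight after Video 2 (Section 2.3, step 3(a)). These precede Video 3 and so isolate carry-over from Video 1. Use the endline SD-H outcomes as support, and note that they combine the influence of the doctors in Videos 1 and 3.

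Keep the interaction, name its comparator cells, and label it as whether the difference between CDC speaker and partner doctor depends on the doctor's concordance. State that its sign on Video 2 and SD-H outcomes is not evidence on hypothesis 1.

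The cost is one extra pre-specified contrast and a few lines of text, with no new data. Under equal cells its standard error is smaller than the interaction's: the interaction SE is √2 = 1.41 times as large against cells 1 and 5, and 0.048/0.041, about 1.15 times before rounding, against all 12 other video cells. The contrast must be counted in the multiplicity adjustment.

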2.3 Experimental Protocols and Treatments

Our experiment has the following structure:

1. Recruitment and Baseline survey
 - (a) Recruit target sample via Lucid
 - (b) For Hispanic respondents, elicit a preference for English or Spanish. Those with a preference for Spanish will be given Spanish language survey questions and will see treatment videos recorded in Spanish as well.⁴
 - (c) Collect demographic information and healthcare experience. Several demographics variables are being collected directly by Lucid.
2. Randomize Subjects to treatment
 - Treatment scripts are tailored to each racial/ethnic group
 - Within racial/ethnic group, treatment is stratified on age, gender and geographic region.
 - Randomization is at the individual level according to Figure 1.
 - There will also be a control group who will receive COVID-19 information at the very end of the survey.
3. Video delivery for all individuals not in the pure control group.
 - (a) After each of the three videos, respondents evaluate the video's usefulness, and trustworthiness, along with the respondents intention to follow the advice in the video and share information from the video.
 - (b) Prior to the third video (masks), individuals will answer questions about second order beliefs about mask wearers.
4. Endline survey
5. Videos shown to the pure control group.
6. Debrief script
7. Follow-up survey
 - (a) We are tentatively planning to follow up with participants several days post-treatment
 - (b) The chief purpose would be to measure health-seeking and health-preserving behaviors.⁵
8. Once we learn which messaging strategy is most effective, we will scale up that treatment more broadly (distributing it through social media etc.)

⁴The one exception is the CDC video with [name]. This is always shown in English.

⁵We do not commit on analyzing this data or even fully implementing a follow up because it is quite difficult to successfully follow up with online survey participants, so it will depend on our success in finding people in our pilot.

3. General Hypotheses to be Tested

This section lists the general hypotheses we want to test. For those, we are planning to run broadly pooled treatments (and specific interactions specified below).

Main hypotheses:

1. What is the overall effect of any combination of videos, compared to the control group?
2. Does racial concordance between the doctor messenger and recipient give the message higher impact across the board?

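### Secondary test 6 (CDC-representative video by elephant content) cannot be estimated under Figure 1, because no randomized cell combines the two

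*Combined protocol and SAP*

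**What the plan says.** Below, the CDC representative is the person whose name is removed from the text, and elephant content is the acknowledgment of inequality in Video 1.

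- **Planned test.** Section 5.3, secondary test 6: "name] treatment effect will be interacted with elephant treatment". Section 3, secondary hypothesis 3, asks whether elephant content lends credibility to other information and adds "Interaction effects with CDC treatment and with mask debiasing treatment".
- **Design.** Section 2.3, item 2: "Randomization is at the individual level according to Figure 1". The caption of Figure 1 in Section 2.1: "There are 8 content-variants for each video, shown here". Each variant comes in a concordant and a discordant form, and Section 5.3 speaks of a large "sample within each of 16 treatment cells".
- **Wording that points the other way.** Section 2.1 introduces its list with "We are varying four aspects of the videos across treatments". Elephant content and the identity of the Video 2 doctor are separate items on that list.
- **Related main contrasts in Section 5.3.** Contrast 3 takes the representative's video without elephant content, and the two elephant versions with "no [name] each compared to the 'no elephant, no [name]' condition". Contrast 4 is "name] versus everything else".

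**The concern.** An interaction between two factors can be estimated only if some participants receive both. Figure 1 treats the representative's video and the two elephant versions as alternatives to one another, not as factors that can be combined. On that design, test 6 asks how elephant content changes the response to a video that nobody saw together with elephant content.

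A pre-analysis plan fixes in advance what will be tested. Here the software would drop the term, or an analyst would have to choose a substitute after the data are in. A comparison of the representative's column with the elephant columns is possible, but it is a difference between two separate effects, not an interaction.

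The same layout affects how main contrast 4 reads. Main hypothesis 4 concerns the same message given by different messengers, yet the comparison group in contrast 4 is mostly made up of cells with elephant content.

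**Working it through.** **1. Reproduce the plan's counts.** Figure 1 has 4 columns and 2 mask rows: 4 × 2 = 8 variants. With 2 levels of concordance, 8 × 2 = 16 cells. Both match the text. Crossing elephant content (3 levels) with the Video 2 messenger (2 levels) would give 3 × 2 × 2 = 12 variants and 12 × 2 = 24 cells, which matches neither.

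**2. Code the columns of Figure 1.** N = CDC representative; E1, E2 = the two elephant versions. Figure 1 does not name the Video 2 messenger in the elephant columns; main contrast 3 describes the elephant versions as without the representative.

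| Column | Cells | N | E1 | E2 | N×E1 | N×E2 |
|---|---|---|---|---|---|---|
| Doctor message | 1, 5 (c/d) | 0 | 0 | 0 | 0 | 0 |
| Representative's message | 2, 6 (c/d) | 1 | 0 | 0 | 0 | 0 |
| Elephant 1 | 3, 7 (c/d) | 0 | 1 | 0 | 0 | 0 |
| Elephant 2 | 4, 8 (c/d) | 0 | 0 | 1 | 0 | 0 |

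Both products are zero in all 16 cells. The pure control group has neither factor and adds only zeros.

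**3. Rank of the design matrix.** The base model has 6 columns: intercept, concordance, mask, N, E1, E2.

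| Added to base | Columns | Rank, Figure 1 (16 cells) | Rank, crossed (24 cells) |
|---|---|---|---|
| Test 1: N × concordance | 7 | 7 | 7 |
| Test 2: N × mask | 7 | 7 | 7 |
| Test 3: E1, E2 × concordance | 8 | 8 | 8 |
| Test 4: mask × concordance | 7 | 7 | 7 |
| Test 5: mask × E1, E2 | 8 | 8 | 8 |
| Test 6: N × E1, N × E2 | 8 | **6** | 8 |
| Test 6 with one pooled elephant term | 7 | **6** | 7 |

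Tests 1 to 5 together need 6 + 1 + 1 + 2 + 1 + 2 = 13 columns and have rank 13 under Figure 1. Adding test 6 gives 15 columns, still of rank 13. In the crossed design the same 15 columns have rank 15. Test 7 uses provider gender, which is not a Figure 1 factor, and was not checked.

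**4. Does the messenger in the elephant columns matter?** No. Four columns supply four means, and the intercept, N, E1 and E2 use all four, so 4 − 4 = 0 degrees of freedom remain for N × E. If the representative delivered Video 2 in both elephant columns, N×E1 would equal E1 and N×E2 would equal E2, and the rank would still be 6. A crossed design has 3 × 2 = 6 means, which leaves 6 − 4 = 2.

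**5. Main contrast 4.** The representative's group is 4 cells, 0 with elephant content. If everything else means the other video cells, it is 16 − 4 = 12 cells, 8 with elephant content. With equal cells and main effects only, the contrast estimates N − (4/12)E1 − (4/12)E2 = N − 0.333·E1 − 0.333·E2. The documents give no allocation ratio. If each elephant column has r times the doctor column (assumed), the elephant share of the comparison group is 2r/(1 + 2r): 0.50 at r = 0.5, 0.67 at r = 1, 0.80 at r = 2.

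**The case against.** The strongest reply is that crossed cells may in fact have been fielded. Section 1 speaks of cross-randomizing, Section 2.1 lists messenger and elephant content as separate aspects, and the qualifiers in main contrast 3 would be largely redundant if the two were never combined. The plan is dated May 14, 2020, one day after the planned start on May 13, so it cannot show what was assigned. This part stands: it is certain that the plan contradicts itself, whereas the impossibility of test 6 is conditional on Figure 1. Figure 1 carries more weight, because randomization is expressly tied to it and both counts agree with it. The contrast 3 qualifiers fit either design.

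The CDC clause of secondary hypothesis 3 is ambiguous. Footnote 4 and Section 5.4 use CDC for the representative's video; Section 5.2 uses it for the content. On the second reading, the elephant arms of main contrast 3 already address the question. That also stands.

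On main contrast 4, the clean comparison for hypothesis 4 (cells 2 and 6 against 1 and 5) is already in contrast 3. Nothing shows that Video 1 content moves the social distancing and hygiene outcomes materially. So the remark on contrast 4 is a matter of definition and reading, not a second failure.

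Finally, a zero term gives no estimate and so cannot give a biased one. The harm is limited to one secondary test.

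**Conclusion.** The concern holds. If randomization followed Figure 1, secondary test 6 is not identified at any sample size, in either racial or ethnic group: 0 of 16 cells combine the two factors, and the rank is 6 for 8 columns. The result needs no assumption about effect size, variance, allocation or control-group size. It rests only on the plan's own link between randomization and Figure 1, which the counts of 8 and 16 support. The CDC clause of secondary hypothesis 3 fails in the same way only if it refers to the representative's video.

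The main contrasts and secondary tests 1 to 5 remain estimable, including mask by elephant. Under Figure 1, the trial cannot say whether elephant content changes the response to the representative's video. The point should be fixed, but it does not threaten the main results.

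**What to change.** First check the implemented assignment against Figure 1. Then reconcile Sections 2.1, 3 and 5.3.

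**If Figure 1 is right:**
- Withdraw secondary test 6.
- Withdraw the CDC clause of secondary hypothesis 3, or define CDC treatment so that it does not mean the representative's video.
- State that the design cannot show whether elephant content changes the response to that video.
- Refer the credibility question to the elephant arms of main contrast 3: each elephant version (cells 3 and 7; cells 4 and 8) against cells 1 and 5, on the social distancing and hygiene outcomes and the Video 2 ratings. Label it a simple effect for the doctor-delivered message only.

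**If crossed cells were fielded:** keep test 6, and correct Figure 1 and the counts of 8 and 16.

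**In either case:** state which cells form the comparison group in main contrast 4, and whether the pure control group is among them. Keep secondary tests 1 to 5.

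The cost is one check of the assignment file and a wording change, with no new arm, participant or outcome. If Figure 1 is right, one secondary question is openly given up.
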